# 6.2.1. Time Period and Frequency for Collecting AE and SAE Information

All AEs should be monitored throughout the study. All AEs and SAEs must be recorded in the eCRF.

All AEs and SAEs will be collected from the signing of the informed consent form until the final study visit.

All SAEs will be recorded and reported to the sponsor or designee within 24 hours of recognition, as indicated in Section 9.3 (Appendix 3). The investigator will submit any updated SAE data to the sponsor within 24 hours of it being available. AEs related to Nucala will be recorded and reported to the sponsor or designee within 5 work days of recognition.

Investigators are not obligated to actively seek AE/SAEs after the conclusion of the study participation. However, if the investigator learns of any SAE, including a death, at any time after a participant has been discharged from the study, and they consider the event to be reasonably related to Nucala, the investigator must promptly notify the sponsor. As for death information, investigators are asked to report it to the sponsor throughout the study period regardless of whether the death is related to Nucala or not.

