The summary be provided for AESI. The percentage will be calculated in two ways; one with number of participants with event as the denominator and the other with total number of participants as the denominator. The worst-case approach will be applied at participant level for the maximum intensity (i.e. a participant will only be counted once as the worst case from all the events experienced by the participant). For action taken to an event, a participant will be counted once under each action (e.g. if a participant has an event leading to both study discontinuation and dose reduction, the participants will be counted once under once under both actions).

Listings of all AEs and of subject numbers for individual AEs will be displayed. Reasons for considering as a SAE, AEs leading to withdrawal from study and AESIs will also be listed. In addition, patient profiles will be provided of patients with deaths.

Exposure-adjusted AE rate (the number of events per 1000 participant-years of exposure) for the AEs will also be summarized. This summary table will be produced by the

observation period and the total period (the observation period and the follow-up period), respectively.

The number of events per 1000 participant-years of exposure will be calculated as:

 $(1000 \times \text{number of AEs during the period}) / (total duration of exposure in days / 365.25)$

The derivation of the total duration of exposure in days is defined in 6.2.3.

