4.3.1.2.3. Annualized Rate of Hospitalization for EGPA-related Events

Endpoint
Annualized rate (event/year) of hospitalization for EGPA-related events

Model Specification

The annualized rate of hospitalization for EGPA-related events will be analyzed by using a negative binomial generalized linear model with logarithm of time as an offset variable, without covariate. The annualized rate and associated 95% CIs will be calculated by exponential transform the value of intercept term and associated 95% CIs estimated when the above model was applied. The annualized rate will be calculated in observation period and retrospective period independently.

Terms in the model:

- **Response**: number of recorded, on-treatment, hospitalization for EGPA-related events experienced per participant.
- Offset: logarithm of treatment time in year

Observation period:

Treatment time in year for each participant will be calculated as:

Participants who complete the study:

 $\{(date of end of Nucala - date of start of Nucala) + 1\} / 365.25$

Participants who enter the follow-up period:

 $\{(date of end of Nucala + 28 - date of start of Nucala) + 1\} / 365.25$

For the raw value of calculation result, round off to two decimal places will be applied.

If the date of end of Nucala is missing, the date of start of the last administration of Nucala + 28 days will be imputed for the date of end of Nucala.

```
Retrospective period:
```

Treatment time in year for each participant will be calculated as:

48 / 52

```
SAS code:
```

```
proc genmod data = <dataset>;
  model n_hosp =
  / link=log dist=negbin offset=logfuinyears;
run;
data parm_est(keep= val rate rate_ll rate_ul);
  set out_parm(where=(parameter='Intercept'));
  format rate rate_ll rate_ul 8.2;
  val= "annualized rate of hospitalization for EGPA-related events
from negative binomial model without covariate";
  rate=exp(estimate);
  rate_ll=exp(lowerwaldcl);
  rate_ul=exp(upperwaldcl);
  run;
```

where n_hosp is the number of hospitalizations for EGPA-related events per participant in follow-up time, and logfuinyears is logarithm of the treatment time in years.

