4.3.1.2.4. Annualized Rate of Emergency Room/Unscheduled Visit for EGPArelated Events

Endpoint

Annualized rate (event/year) of emergency room/unscheduled visit for EGPA-related events

Model Specification

The annualized rate of emergency room/unscheduled visit for EGPA-related events will be analyzed by using a negative binomial generalized linear model with logarithm of time as an offset variable, without covariate. The annualized rate and associated 95% CIs will be calculated by exponential transform the value of intercept term and associated 95% CIs estimated when the above model was applied. The annualized rate will be calculated in observation period and retrospective period independently.

Terms in the model:

- **Response**: number of recorded, on-treatment, emergency room/unscheduled visit for EGPA-related events experienced per participant.
- **Offset**: logarithm of treatment time in year

Observation period:

Treatment time in year for each participant will be calculated as:

Participants who complete the study:

{(date of end of Nucala – date of start of Nucala) + 1} / 365.25

Participants who enter follow-up period:

 $\{(date of end of Nucala + 28 - date of start of Nucala) + 1\} / 365.25$

For the raw value of calculation result, round off to two decimal places will be applied.

If the date of end of Nucala is missing, the date of start of the last administration of Nucala + 28 days will be imputed for the date of end of Nucala.

Retrospective period:

Treatment time in year for each participant will be calculated as:

48 / 52

SAS code:

proc genmod data = <dataset>;

```
model n_emv =
/ link=log dist=negbin offset=logfuinyears;
run;

data parm_est(keep= val rate rate_ll rate_ul);
set out_parm(where=(parameter='Intercept'));
format rate rate_ll rate_ul 8.2;
val= "annualized rate of emergency room/unscheduled visit for
EGPA-related events from negative binomial model without
covariate";
rate=exp(estimate);
rate_ll=exp(lowerwaldcl);
run;
```

where n_emv is the number of emergency room/unscheduled visit for EGPA-related events per participant in follow-up time, and logfuinyears is logarithm of the treatment time in years.

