6.2.2. Study Period

Assessments and events will be classified according to the time of occurrence relative to the study period.

Screening period is defined as 0-4 weeks before the date of dose of Nucala at Week 0.

Observation period is defined as time from the date of dose of Nucala at Week 0 to the stop date of Nucala +28 days for the participants who did not withdraw from study, or the first treatment discontinuation date +28 days for the participants who withdraw from study. If the date of dose of Nucala at Week 0 is missing, the latest available date between the screening visit date and the Week 0 visit date will be used for the start date of the observation period. When the last Nucala stop date is missing, the last Nucala start date will be imputed.

Follow-up period is defined as time from the first treatment discontinuation date +29 days to 96 weeks within the observation period at maximum. The follow-up period is only applicable for the participants who discontinued the treatment.

Retrospective period is defined as time (within 12 weeks) before the first dose of Nucala. For data of hospitalization for EGPA-related events and ER/Unscheduled visit for EGPA-related events the period is defined as time (within 48 weeks) before the first dose of Nucala.

The study periods to use for summaries on each endpoint are as below.

A:	PMS period	B: Observation period
Retrospective		
period		

Participants who completed the study

Participants who discontinued and moved to the follow-up period

C:	PMS period	D: Observation	E: Follow-up
Retrospective		period	period
period			

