6.2.3. Study Day and Nucala Stop Date

The study day will be calculated relative to visit date of Week 0 and as the number of days from Week 0:

- Ref Date = Missing then Study Day = Missing
- Ref Date < Week 0 then Study Day = Ref Date Week 0
- Ref Date \geq Week 0 then Study Day = Ref Date (Week 0) + 1

The duration of exposure to Nucala is calculated as (Nucala stop date – Nucala start date + 29). If overall Nucala stop date is missing, the last Nucala start date will be imputed.

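### The total-period AE rate counts follow-up AEs but gives untreated follow-up no person-time, and the follow-up AE summary required by the protocol is dropped undeclared

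*SAP*

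**What the plan says.** **Rate.** SAP 4.2.2 plans a rate per 1000 participant-years for two rows, the observation period and the total period. The numerator is the "number of AEs during the period". For the denominator it says only: "The derivation of the total duration of exposure in days is defined in 6.2.3".

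**Denominator.** SAP 6.2.3 has a single formula with no version by period: "The duration of exposure to Nucala is calculated as (Nucala stop date – Nucala start date + 29" days). It adds: "If overall Nucala stop date is missing, the last Nucala start date will be imputed".

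**Periods.** SAP 6.2.2 runs the observation period from the Week 0 dose to 28 days after stopping. Then: "Follow-up period is defined as time from the first treatment discontinuation date +29 days to 96 weeks". Only participants who discontinued Nucala have a follow-up period.

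**AE collection.** Protocol 6.2.1: "All AEs and SAEs will be collected from the signing of the informed consent form until the final study visit". AEs in follow-up are therefore collected.

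**Summaries.** Protocol 4.5 asks for the AE summary in three versions: observation, follow-up and total. SAP 4.2.2, and the subgroup AE summaries in SAP 4.6.4, give observation and total only. SAP 4.8 states that nothing changed from Protocol Amendment 01.

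**The concern.** A rate needs events and time from the same window. Here the total-period events come from observation plus follow-up, while the time comes from exposure alone. If the rate is meant to be on-treatment, AEs after the exposure window do not belong in it. If it is meant to describe study time, the untreated follow-up days do.

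The two rows will be read side by side. If the same duration is used in both, as the text reads, the total row has at least as many events over the same time. It then cannot fall below the observation row, even if AEs become rarer after stopping.

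The missing follow-up summary is a separate matter. It is the only planned protocol table that would show AEs after stopping on their own, and its removal is not declared.

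**Working it through.** **Plan's own figures.** The documents state no AE rate, person-time or discontinuation fraction. Their only calculation, the sample size, reproduces: the smallest n with 1 − 0.985^n at or above 70%, 80% and 90% is 80, 107 and 153, and 107/0.9 ≈ 119, given as approximately 120.

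**Do the windows meet?** Exposure of stop − start + 29 days covers start to stop + 28 inclusive. Follow-up opens at first discontinuation + 29. Without re-treatment, exposure days equal observation days and no follow-up day is in the denominator.

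**Size.** Assumptions: the start date in SAP 6.2.3 is the Week 0 dose; completers contribute C = 673 days (last dose Week 92: 7 × 92 + 29); follow-up is complete to Day 673; no re-treatment. A fraction f stops at Week t.

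- Discontinuer's exposure: 7t + 29 (Week 48: 365; Week 72: 533)
- Observation time per participant: O = (1 − f) × C + f × (7t + 29)
- Omitted follow-up time per participant: F = f × (673 − 7t − 29)
- Overstatement: (O + F)/O − 1 = F/O, whatever the AE rate

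| Stopping | O (days) | F (days) | Overstatement |
|---|---|---|---|
| 5% at Week 72 | 666.0 | 7.0 | 1.1% |
| 10% at Week 72 | 659.0 | 14.0 | 2.1% |
| 5% at Week 48 | 657.6 | 15.4 | 2.3% |
| 10% at Week 48 | 642.2 | 30.8 | 4.8% |
| 20% at Week 48 | 611.4 | 61.6 | 10.1% |

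With 120 participants and 12 stopping at Week 48, the omitted time is 12 × 308/365.25 = 10.1 participant-years, beside (108 × 673 + 12 × 365)/365.25 = 211.0 of exposure.

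**Direction.** Let 10% stop at Week 48 and the AE rate then halve.

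- Reported total/observation: 1 + 0.5 × 30.8/642.2 = 1.024
- Matched total/observation: (642.2 + 0.5 × 30.8)/673 = 0.977

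The table would show the total 2.4% above the observation rate when it is 2.3% below.

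**Two dates left open.**

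- *Stop date.* Re-treated participants stay in follow-up (Protocol 3.1). SAP 6.2.2 starts follow-up at the first discontinuation, while SAP 6.2.3 speaks of an overall stop date. Take a stop at Week 24, a restart at Week 60 and a last dose at Week 92. Time to the first stop is 24 × 7 + 29 = 197 days; to the overall stop it is 92 × 7 + 29 = 673 days; time on drug is 197 + (32 × 7 + 29) = 450 days. Under the overall-stop reading, the off-drug gap counts as exposure and the observation period can overlap follow-up.
- *Start date.* SAP 6.2.3 does not say that it is the Week 0 dose, although SAP 6.2.4 specifies Week 0 when it means that. Week 0 is the natural reading. If the first-ever EGPA dose were meant, at least 672 days per participant would be added, and the 4.8% would fall to about 30.8/(642.2 + 672) = 2.3%.

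**The case against.** **The measure is exposure-adjusted by name.** Protocol 4.5 asks for an exposure-adjusted rate and SAP 4.2.2 labels it per participant-years of exposure, so untreated time is arguably excluded on purpose. That explains the denominator but not the follow-up AEs above it. Reading exposure separately by period adds only re-treatment days and still leaves out untreated follow-up.

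**It matters little.** This largely stands. The primary endpoints are AE frequencies, the rate is an additional summary, and nothing is tested. The error raises the reported rate rather than hiding events. Entrants had at least 96 weeks of Nucala and a physician's decision to continue, so few may stop. Only those who stop and remain under follow-up contribute, and nothing in the documents supports 10% or 20% in particular.

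**Three stronger readings do not hold.**

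- A reader might infer that information on AEs after stopping is lost. Follow-up event counts can be obtained by subtracting the two tables, and the participants can be identified from the AE listings planned in SAP 4.2.2. What is missing is a tabulated summary and a rate.
- A reader might cite the hospitalization and emergency-visit rates as showing that the SAP matches events to time elsewhere. They do name on-treatment events ("number of recorded, on-treatment, hospitalization for EGPA-related events experienced per participant"), but that term is not defined there. For completers the time is "date of end of Nucala – date of start of Nucala) + 1} / 365.25", without the 28 days that SAP 6.2.2 includes, and the code notes describe the counts as falling in follow-up time. They are not a clean model.
- A reader might infer that correcting the rate always lowers it. Adding follow-up time does, but stopping the clock at the final visit can work the other way, as shown under the fix.

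**Conclusion.** The mismatch is on the face of the text: SAP 4.2.2, 6.2.2 and 6.2.3 together count follow-up AEs without untreated follow-up time. This is exact for participants who are not re-treated; for re-treated participants it depends on a stop date the SAP does not specify. The undeclared omission of the follow-up summary is equally plain and needs no assumption.

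The size is conditional. Under the assumptions listed, the total rate is overstated by 1.1% to 10.1% across the five scenarios, and by little if few participants stop. Incomplete follow-up, re-treatment or another start date would change these figures.

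A reader might infer that the safety results as a whole are biased. They are not: the defect is confined to the total-period rate, its comparison with the observation rate, and one missing table. It should be fixed because a reported safety rate has no clear meaning as written and the repair is cheap.

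**What to change.** **Person-time (SAP 4.2.2 and 6.2.3).** Define time to match each numerator:

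- Observation: Week 0 dose to the end of the observation period in SAP 6.2.2, but not past the final study visit, when AE collection ends.
- Follow-up: first discontinuation + 29 days to actual study exit.
- Total: the sum, labelled as participant-years of study time (observation plus follow-up). This changes the protocol's exposure measure, so record it in SAP 4.8.

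A smaller alternative is to report the exposure-adjusted rate for the observation period only, and record that in SAP 4.8.

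**Dates.** State that the start date is the Week 0 dose and which stop date applies to re-treated participants, so that each day and each AE falls in one period only.

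**Follow-up summary.** Restore the follow-up AE summary of Protocol 4.5, or record its omission in SAP 4.8.

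**Cost.** SAP wording, one derived variable and one table; no new data.

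**Effect on the numbers.** If completers are credited 701 days (stop date at Week 96: 7 × 96 + 29) and the final visit is Day 673, the cap removes up to 28 days and can raise both rates. The corrected total is then 673 days for everyone, against current values of O = 692.6, 684.2, 684.2, 667.4 and 633.8 in the five scenarios. Corrected over current rate = O/673 = 1.029, 1.017, 1.017, 0.992 and 0.942, a net change from +2.9% to −5.8%.

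A follow-up rate will be imprecise. For example, 5 AEs in 10.1 participant-years is 494 per 1000, exact Poisson 95% CI 160 to 1153. Show it with its interval.

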4.2.3. Sensitivity analyses

Not Applicable

4.3. Secondary Endpoint(s) Analyses

4.3.1. Secondary endpoint(s)

4.3.1.1. Definition of endpoint(s)

The secondary endpoints are as follows:

- Proportion of participants with clinical symptoms as assessed by 9 organ-systems (i.e. systemic, skin, mucous membranes/eyes, ears/nose/throat, chest, cardiovascular, abdominal, renal, nervous system)
- Proportion of participants with EGPA relapse
- Annualized rate (event/year) of hospitalization for EGPA-related events
- Annualized rate (event/year) of emergency room/unscheduled visit for EGPA-related events
- Average daily dose (prednisolone-equivalent) of oral corticosteroid (OCS) over the observation period
- The proportion of participants in the dosing categories^{*} relative to average daily OCS (prednisolone-equivalent) over the observation period
 * 0 mg/day, 0 mg/day < ≤ 4.0 mg/day, 4.0 mg/day < ≤ 7.5 mg/day, 7.5 mg/day <

4.3.1.2. Main analytical approach

The secondary analyses will be based on the TP. All endpoints will be summarized by using appropriate descriptive statistics.

4.3.1.2.1. Clinical Symptoms as Assessed by 9 Organ-systems

Endpoint

Proportion of participants with clinical symptoms as assessed by 9 organ-systems

Specification

The frequency and percentage of participants with clinical symptoms as assessed by each of 9 organ-systems will be summarized for each assessment time point (Retrospective period and Week 0: "none", "active", Week 12 and after: "none", "active", "worsening", "active + worsening"). The frequency and percentage of participants without clinical symptoms as assessed by 9 organ-systems will be summarized for each assessment point. Patients with at least one "worsening" at each assessment point will also be summarized. In addition, line plots will be produced by 9 organ-systems. They will be displayed for the observation period and by the follow-up period separately.

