#### Follow-up period

The follow-up period is only applicable to participants who have discontinued the treatment of Nucala due to any reason. The assessments in the routine clinical practice during the follow-up period are shown in Section 9.1 (Appendix 1).

In case EGPA symptoms are deteriorated in a participant who previously discontinued the treatment of Nucala due to improvement of EGPA symptoms, the participant can receive the re-treatment of Nucala during the follow-up period. The participant who received the re-treatment of Nucala continues the assessments in the follow-up period.

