#### 9. APPENDIX

# 9.1. APPENDIX 1: SCHEDULE OF ACTIVITIES (SOA)

Procedure	Screening		Observation period			Follow-up 
Time period for which data should be collected at	Up to 4 we	eks before Week 0 	Week 0	Week 12 to 96;	Early	Up to 96 weeks
usual EGPA healthcare visits,	(Screening  )	(Retrospective data 	Baseline	no more frequently than	withdrawal	after Week 0
if this is possible		collection)		every 12 weeks (±4weeks)		
Informed consent	X 					
Inclusion and exclusion criteria	Χ					
Demography	X					
Administration status of Nucala for EGPA	X		Χ	Χ	Χ	X 5
Concomitant medication	X	X6	Χ	Χ	Χ	X
Concomitant therapies	X	X 	Χ	X	Χ	X
Adverse events	X		+			→
Clinical symptoms		Χ	Χ	Χ	Χ	X
Hospitalization for EGPA-related events		X8	Χ	X	Χ	X
ER/Unscheduled visit for EGPA-related events		X8	Χ	Χ	Х	X
Asthma exacerbation		X8	Χ	Χ	Х	X
Clinical laboratory parameters  , if performed		Х	Χ	Χ	Χ	X
Lung function, if performed		Х	Χ	X	Χ	X
Ejection fraction, if performed		Х	Χ	Χ	Χ	X
Pregnancy reporting			•		-	
EGPA recurrence						X

- 1. The follow-up period is only applicable for participant who discontinued the treatment. If drug-related adverse events occurred, contact the sponsor.
- 2. Screening and Week 0 can occur on the same day.
- 3. Retrospective data within 12 weeks (otherwise specified) before the first dose of Nucala for EGPA.
- 4. Informed consent must be obtained prior to start of any study's procedure.
- 5. Only for in case of receiving the re-treatment of Nucala.
- 6. Only for other biological products, Nucala for asthma, corticosteroid, immunosuppressants, and immunoglobulin.
- 7. Only for EGPA therapies.
- 8. Number of events within 48 weeks before the first dose of Nucala for EGPA.
- 9. Haematological parameters tested are:

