	[approxi	mately	y 2 yea	rs] bef	fore). T	hese ret	rospect	tive dat	ta shou	ld be fr	om

	physician source/medication record. By using the retrospective data, information could be provided about the change from pre-Nucala exposure to the end of this study, of which a period would be approximately 4 years.
	Any participant who completes assessments during the screening period but does not continue in the study beyond Baseline or is subsequently found to be ineligible for the study prior to Baseline, is classified as Screen Failure. Information collected for the participant classified as Screen Failure is detailed in the guideline for eCRF entry. Re-screening is permitted once only.
	Observation period:
	During the observation period, which is scheduled for 96 weeks (approximately 2 years) at maximum, safety and effectiveness data are obtained at approximately 12-week intervals. The intervals may be shorter/longer or may be irregular depending on the usual pattern of healthcare visits.
	Any data collected during the observation period are entered into eCRF. The assessments in the routine clinical practice during the observation period are shown in the protocol Section 9.1 (Appendix 1).
	Follow-up period:
	The follow-up period is only applicable to participants who have discontinued the treatment of Nucala due to any reason. The assessments in the routine clinical practice during the follow-up period are shown in the protocol Section 9.1 (Appendix 1).
	In case EGPA symptoms are deteriorated in a participant who previously discontinued the treatment of Nucala due to improvement of EGPA symptoms, the participant can receive the re-treatment of Nucala during the follow-up period. The participant who received the re-treatment of Nucala continues the assessments in the follow-up period.
Study interventio n Assignment	Not Applicable
Interim Analysis	The purpose of the interim analysis that for present results of the analysis for the primary outcome of the long-term safety of Nucala, and the secondary outcomes of the long-term effectiveness of Nucala using dataset including data until 48 weeks post-exposure. This analysis does not lead to a decision to amend the design or to stop the study.
	The interim analysis is carried out using interim dataset.
	All required database cleaning activities in accordance with the Data Management Plan (DMP) have been completed and interim database lock (DBL) has been declared by Data Management.

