4.3.1.2.2. EGPA Relapse

Endpoint

Proportion of participants with EGPA relapse

Specification

The frequency and percentage of participants with EGPA relapse for the observation period and for the follow-up period will be summarized. The frequency and percentage of participants with EGPA relapse will be categorized as 1 time, 2 times, and \geq 3times, and summarized. The frequency and percentage of EGPA relapse and the events that cause EGPA relapse (1-3 in the Step1 below) will also be summarized. A separate summary will be displayed for the events that cause EGPA relapse. A listing of EGPA relapse will also be produced.

Determination of EGPA relapse

EGPA relapse is defined as any of the following events with worsening EGPA*

- 1) Increased dose of OCS
- 2) Initiation/increased dose of immuno-suppressive agents**
- 3) EGPA treatment with hospitalization

* Worsening of EGPA: new onset of EGPA symptoms or worsening of existing clinical symptoms as assessed by 9 organ-systems.

** Immuno-suppressive agents: If the dose of immuno-suppressive agents increases for the same formulation or if the number of immuno-suppressive agents increases for EGPA treatment.

Event date is defined as:

- 1) Increased dose of OCS: **Date of increased dose**
- 2) Initiation/increased dose of immuno-suppressive agents: Date of initiation/Date of increased dose
- 3) EGPA treatment with hospitalization: Date of hospitalization

The first relapse occurred between two consecutive assessment time points will be counted as EGPA relapse for the first of the two assessment points. When assessment time points are scattered (i.e. Week 24 data is missing due to no clinic visit), events occurred within the last visit date + 84 days will be used as the determination for EGPA relapse.

Definition of Relapse Date

Set the starting point date for each of the following relapse conditions 1) to 3) and calculate the time to relapse (day).

The formula for calculating the time to relapse is relapse date – starting point date + 1

However, if the conditions 1) to 3) overlap, the shortest time (day) until relapse will be used.

1) Increase in OCS dose

- The date of relapse is the date of dose increase.
- The starting point date is the date of the end of dosing immediately before the dose increase or the earliest assessment date without symptoms of EGPA and dose reduction.

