4.5. Other Safety Analyses

4.5.1. Extent of Exposure

The frequency and percentage of exposure to Nucala will be summarized for each of the following categories by the observation period and the follow up period, based on the TP. The extent of exposure will also be listed.

- Nucala 300mg SC only
- Other than the above (e.g., dose reduction of Nucala)

The duration in days between the first dose of Nucala for EGPA in the retrospective period and the last dose of Nucala in the observation period will be summarized.

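### The follow-up symptom and relapse displays mix time back on Nucala with time off it, so they describe status after first stopping, not off-drug status

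*SAP*

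**What the plan says.** **Who may restart, and where they are counted.** Protocol 3.1 (Follow-up period) covers a participant who stopped because EGPA had improved and then got worse: "the participant can receive the re-treatment of Nucala during the follow-up period". SAP 1.2 repeats this and adds: "The participant who received the re-treatment of Nucala continues the assessments in the follow-up period".

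**How the period is bounded.** SAP 6.2.2: "Follow-up period is defined as time from the first treatment discontinuation date +29 days to 96 weeks within the observation period at maximum". Nothing ends or divides it at a restart. The follow-up visit windows in SAP 6.2.4 run from Follow Week 0 to Follow Week 96, also without reference to a restart.

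**How the endpoints are shown.** For symptoms, SAP 4.3.1.2.1 says "They will be displayed for the observation period and by the follow-up period separately". For relapse, SAP 4.3.1.2.2 says "The frequency and percentage of participants with EGPA relapse for the observation period and for the follow-up period will be summarized". Protocol 4.6 plans the summary tables by the same two periods. Neither SAP section mentions re-treatment.

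**Exposure.** SAP 4.5.1 tabulates exposure by period in two rows: the 300 mg subcutaneous regimen alone, and a second row reading "Other than the above (e.g., dose reduction of Nucala".

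**What is recorded.** The Schedule of Activities (Protocol Appendix 1) collects Nucala administration status in follow-up, with footnote 5: "Only for in case of receiving the re-treatment of Nucala".

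**The concern.** The observation period is time on Nucala, and a participant enters follow-up by stopping it. A reader who sees the two displays side by side will naturally compare on drug with off drug. Protocol 3.3.3 encourages that reading, since it justifies follow-up by the wish to learn about safety and effectiveness in those who stopped. Protocol 4.6 also has an objective on whether response holds after stopping.

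The follow-up column does not isolate off-drug time. It also holds visits and relapses of participants who are back on Nucala. The mixing is selective, because the only stated route to a restart is deterioration after stopping for improvement. If re-treatment helps these participants, their later visits lower the symptom percentage in a column that may be read as off-drug. Any relapse they have after restarting is counted as a relapse after stopping, with nothing to show that they were on Nucala at the time.

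**Working it through.** The plan gives no figure for how many participants will stop or restart, so there is nothing to reproduce on this point. All counts and rates below are assumptions that show direction and range.

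**Step 1. Does the pooling follow from the text?** Restart is allowed within follow-up (Protocol 3.1). The restarted participant stays there (SAP 1.2). Follow-up runs from the first discontinuation to Week 96 (SAP 6.2.2). The displays split by period only (SAP 4.3.1.2.1 and 4.3.1.2.2). Post-restart visits and relapses therefore fall in the follow-up display. SAP 6.2.2 ends the observation period 28 days after the Nucala stop date for participants who stayed in the study. For a restarted participant this could be read as the last stop date. The observation period would then overlap follow-up, but follow-up would still contain the re-treated time.

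**Step 2. Symptoms at a visit.** Let *f* be the share of assessed follow-up participants who are back on Nucala, and let *p_off* and *p_on* be the symptom proportions in the two groups.

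Displayed proportion = (1 − *f*) × *p_off* + *f* × *p_on*

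| Assumed *p_off* / *p_on* | *f* = 0 | 10% | 25% | 50% |
|---|---|---|---|---|
| 60% / 30% | 60% | 57% | 52.5% | 45% |
| 80% / 30% | 80% | 75% | 67.5% | 55% |
| 50% / 50% | 50% | 50% | 50% | 50% |

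For example, 0.75 × 60% + 0.25 × 30% = 52.5%. The display is below the off-drug figure only when *f* > 0 and *p_on* < *p_off*.

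**Step 3. Relapse.** Assume 12 participants in follow-up. Eight never restart, and 3 of them relapse; 4 restart. Of those 4, let *k* relapse before restart and let *m* relapse for the first time after it.

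- Pooled: (3 + *k* + *m*) / 12
- Cut at restart: (3 + *k*) / 12

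| *k* | *m* | Pooled | Cut at restart |
|---|---|---|---|
| 0 | 0 | 3/12 = 25% | 3/12 = 25% |
| 0 | 2 | 5/12 = 42% | 3/12 = 25% |
| 0 | 4 | 7/12 = 58% | 3/12 = 25% |
| 4 | 0 | 7/12 = 58% | 7/12 = 58% |

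Pooling never gives a lower ever-relapsed proportion than the cut.

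**Step 4. Would dropping re-treated participants repair it?** Assume 12 in follow-up, 3 re-treated, and 4 of the other 9 symptom-free.

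- Pooled, the 3 become symptom-free: 7/12 = 58% symptom-free
- Pooled, the 3 stay symptomatic: 4/12 = 33%
- Only those still off Nucala: 4/9 = 44% in both cases
- Had the 3 stayed off Nucala with symptoms: 4/12 = 33%

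The off-Nucala group alone is selected too, because it has lost those who deteriorated and restarted. Neither number can be read without the other.

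**The case against.** The strongest reply is that the pooled display is legitimate. It describes what happens after first stopping, whatever follows, and the period definition applies this consistently. The documents never call it an off-drug display. This stands, and it is why the pooled display should be kept. What is missing is a label saying so and a way to see the off-drug part.

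The plan also has a separate analysis of what happens after stopping: Kaplan-Meier time to recurrence (Protocol 4.6). It is a first-event analysis and is largely unaffected by a later restart. However, it is limited to participants who stopped for improvement, and it does not show symptoms over time. SAP 4.4 is redacted and may hold a re-treatment rule for exploratory endpoints, but the symptom and relapse sections are visible and have none.

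Three stronger readings are tempting, and the documents do not support them.

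- **Pooling makes relapse after stopping look better.** Relapses before restart are still counted, and later ones can only add. A deterioration handled by restart alone is not a relapse under SAP 4.3.1.2.2, and cutting at restart would not make it one.
- **The percentage base for follow-up relapse is the whole Treated Population.** SAP 4.3.1.2 does say "The secondary analyses will be based on the TP", and on that base 4 relapsers among 12 in follow-up would show as 4/120 = 3.3% instead of 4/12 = 33%. But that sentence names the analysis set. SAP 6.2.2 restricts follow-up to those who discontinued, and SAP 6.1.1 counts those who entered it. Where the Treated Population is the denominator, for the OCS categories in SAP 4.3.1.2.5, the SAP says so.
- **Restarts cannot be identified from the planned output.** Anyone in the 300 mg row for follow-up must have restarted, and exposure and relapses are also listed by participant. The narrower fault is that the exposure table has no row for participants receiving no Nucala.

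**Conclusion.** The point holds in this form. The follow-up displays show status after first discontinuation regardless of restart, and they are not labelled that way. Visit-level symptom prevalence can be lower than it is off Nucala, provided that some participants restart and that re-treatment helps them. For relapse the fault is attribution: events on re-treatment are counted with events off Nucala.

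The size cannot be stated. With a quarter back on Nucala, the assumed rates in Step 2 give a gap of 7.5 to 12.5 percentage points; with no restarts, or equal rates, the gap is zero. Restarts may be few. Entry requires at least 96 weeks of continuous use and a physician's decision to continue, and a restart requires stopping for improvement followed by deterioration. These are secondary descriptive displays, and Protocol section 5 already warns that effectiveness data will be thin. This is an inexpensive improvement to reporting and does not touch the study's primary safety analysis.

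**What to change.** **SAP 4.3.1.2.1 and 4.3.1.2.2**

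- Keep the pooled follow-up display and label it *after first discontinuation, regardless of re-treatment*.
- At each follow-up time point, add the rows *off Nucala* and *re-treated*, using a flag derived from the first re-treatment date.
- Beside these rows, report the cumulative number re-treated and their symptom status at the last visit before restart, so that the off-Nucala row is not read without those who deteriorated and left it.
- Classify each follow-up relapse as before or after restart.
- State that the percentage base is participants who entered follow-up, and print the number in each row.

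**SAP 4.5.1**

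- Give the follow-up exposure table the rows *no Nucala* and *re-treated with Nucala*.

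**Cost.** SAP wording, one derived flag and a few extra table rows. Data collection, study design and clinical care do not change. The cells will be small, and the off-Nucala row remains a selected group, which a footnote should say.
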